The broad, long range goal of SHARE is to establish a collaborative network of institutions in South Asia, to carry out and to utilize research that answers policy relevant questions related to reducing the treatment gap for mental disorders in the region. SHARE aims to be a driver to facilitate evidence-based mental health policy and program implementation in one of the world's most populous regions with weak health systems and poor social development indicators.

As a result of this collaborative network currently HDRF in partnership Sangath (India) are to implement an RCT (Randomized Control Trial) study coined "SHARE – THPP (Thinking Healthy Program implemented by peer volunteers)."

The goal of this study is to rigorously evaluate the impact of SHARE THPP perinatal depression intervention delivered by peers that starts prenatally and continues through 6 months post-partum, on child development. We will achieve this by conducting a cohort study that is integrated with the intervention clustered RCT, also being implemented by HDRF.

The SHARE THPP includes individual and community-wide components and follows mothers with prenatal depression until 6 months postpartum. Our project, SHARE CHILD, builds on this trial in several critical ways. We (1) focus on child outcomes, (2) extend follow-up to 36 months postpartum, and (3) investigate factors that mediate and modify the effect of the intervention on child outcomes. A unique

window of opportunity is made possible due to the summer 2014 enrollment start date of the SHARE trial.

In addition to enrolling the depressed women who will participate in the SHARE trial, we will also enroll a control group of non-depressed women, and follow-up the mother-child dyads for at least 36 months post-partum. Enrolling the non-depressed mothers enables us to determine the extent to which the intervention can lead to equivalence between the treated depressed and non-depressed groups as well as to identify potential positive externalities to non-depressed women in the intervention arm.

The overall goal of the project is to follow-up families that participated in the SHARE THPP intervention and see whether the intervention has a positive impact on the cognitive and socioemotional development of their children. This larger goal can be broken down into the following objectives:

1. Enroll SHARE THP study participants and perinatally non-depressed women.

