2.1 Principal research objectives and hypotheses to be addressed

The primary objective of the study is to evaluate the impact of a 36-month perinatal peer-delivered community-based perinatal depression intervention on (a) maternal depression and (b) child development. Our primary hypothesis for the perinatally depressed mothers is that the intervention will result in lower prevalence of depression at three years postnatal. Our primary hypothesis for the children is that the perinatal depression intervention will lead to improved developmental outcomes (see measures and constructs in Table 1) at three years of age. Additional child hypotheses address proposed mediators and moderators of the effects of the perinatal depression intervention on child outcomes; however, the mediators will be analyzed as part of a separate paper and so are not included in this document.

The second objective is to determine whether outcomes of perinatally depressed mothers and children in the intervention arm will converge to those in the reference group of perinatally non-depressed mothers and children as well as, secondarily, to determine whether there are any carryover effects of the intervention to benefit perinatally non-depressed mothers and children.

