2.4 Sample size calculation

Much of the following is copied or adapted from the THPP+ protocol paper.¹

The primary power calculations for the THPP+ study are for the c-RCT comparisons of perinatally depressed women and their children in the control vs. intervention arms at 36 months postnatally at the 5% two-tailed significance level. As with the THPP trial,² we assume 40 village clusters randomized in a 1:1 allocation ratio within 11 union councils with 14 perinatally depressed women per village cluster to yield a total sample size of 560 perinatally depressed women at baseline. In addition, for THPP+, we recruit 14 perinatally non-depressed women per village cluster for a total of 560 perinatally non-depressed women at baseline. We conservatively estimate that loss to follow-up (including infant mortality and maternal illness and death) of both perinatally depressed and perinatally non-depressed women at 36 months will be 20%. Therefore, the total sample size available at 36 months is anticipated to be 480 perinatally depressed and 480 perinatally non-depressed women and their children. Using standard formulae^{3,4} for a cluster randomized design and assuming intra-cluster correlation of 0.07 in the intervention arm and 0.05 in the control arm, the trial will have 90% power at 36 months to detect a difference in perinatally depression remission of 65% in perinatally depressed-Intervention vs. 45% in perinatally depressed-control for the anticipated total sample size of 480 perinatally depressed women at 36 months. For child outcomes, this sample size will yield power of more than 90% to detect a difference between arms in mean total difficulties (TD) score (range 0-40) of 3 points for children of perinatally depressed mothers using plausible estimates for intra-cluster correlations of 0.04-0.08⁵ and 5.2 for standard deviation for the TD score among 3 year olds.⁶

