Secondary comparisons mainly focus on child outcomes and are well powered. For the secondary hypothesis of equivalence between children of perinatally depressed mothers in the intervention arm and perinatally non-depressed mothers in the control arm, we will conclude equivalence if the 95% CI for the difference between the mean score in the two groups lies between -2 and 2 units. We note that differences of 1.0-2.0 points are often observed between boys and girls^{6,7}. With 220 children in each group and conservatively assuming an overall significance level of 2.5% (corresponding to the 95% CI), an SD of 5.2 and ICC of 0.04, and no difference between the groups, we will have 83% power to conclude equivalence.^{3,8} For the secondary research question of the community benefit (i.e. carryover) of the intervention for perinatally non-depressed women and their children, we will have 80% power to detect a 1.7 or greater impact of the intervention on mean TD score (Groups perinatally non-depressed-Intervention vs. perinatally non-depressed-Control, Figure 1) for the same assumptions of the primary comparison above.

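### The ±2-point equivalence rule is sound for saying two group means are close, but it is the only criterion for the convergence objective and does not use the depressed-control group, so it cannot by itself show that the intervention closed a gap.

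*SAP*

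**What the plan says.** SAP 2.1 gives the second objective as "to determine whether outcomes of perinatally depressed mothers and children in the intervention arm will converge to those in the reference group", meaning the women who were not depressed perinatally and their children. Protocol section 2 states the same aim causally: the non-depressed women are enrolled to "determine the extent to which the intervention can lead to equivalence between the treated depressed and non-depressed groups".

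SAP 2.4 makes this operational for children as "equivalence between children of perinatally depressed mothers in the intervention arm and perinatally non-depressed mothers in the control arm", with the decision rule "we will conclude equivalence if the 95% CI for the difference between the mean score in the two groups lies between -2 and 2" units. The stated operating characteristic is "an SD of 5.2 and ICC of 0.04, and no difference between the groups, we will have 83% power to conclude equivalence", with 220 children per group.

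Two other parts of the SAP bear on the point. SAP 2.4 makes depressed-intervention versus depressed-control the primary comparison, powered for a 3-point difference. SAP 3.1 fits all groups in one model, and 3.1.1 gives that model three groups, with non-depressed women from both arms in a single category. Neither section says how the equivalence conclusion should be read in light of the primary contrast.

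**The concern.** Convergence implies that a gap existed and that the intervention closed it, wholly or largely. Only the depressed-control group shows where depressed-group children would have been without the intervention, and the rule does not use it. If the intervention does nothing, the difference being tested is simply the untreated gap. Should that gap be small, the interval can sit inside ±2 with no contribution from the intervention.

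At stake is the interpretation of a named secondary hypothesis. Without a stated link to the primary contrast, an equivalence finding could be presented as the answer to the convergence objective even when the primary child result is null.

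**Working it through.** **Inputs from SAP 2.4.** Margin M = 2; 220 children per group; SD 5.2; ICC 0.04 for the equivalence calculation (0.04 to 0.08 is called plausible for the primary child comparison); "40 village clusters randomized in a 1:1 allocation ratio within 11 union councils". That gives 20 clusters per arm and 220/20 = 11 children per cluster per group.

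**Input not in the documents.** The SDQ-TD gap g at 36 months between depressed-control and non-depressed-control children. I assume a range of 0 to 3 points.

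**Step 1: standard error.** SE = 5.2 × √(2 × DE/220), with DE = 1 + 10 × ICC.
- ICC 0.04: DE = 1.4, SE = 0.587.
- ICC 0.08: DE = 1.8, SE = 0.665.

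**Step 2: reproduce the plan's 83%.** The probability that the 95% CI lies inside ±2 when the true difference is g is

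Φ((2 − g)/SE − c) + Φ((2 + g)/SE − c) − 1.

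At g = 0 and ICC 0.04, 2/0.587 = 3.41.
- With c = 1.96 the result is 85.3%.
- With c = 2.024 (t on 40 − 2 = 38 df) it is 2Φ(1.385) − 1 = 83.4%. Using t tails in place of Φ gives 82.6%.

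The stated 83% therefore reproduces with a cluster-level small-sample correction.

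**Step 3: set the intervention effect to zero.** The true difference is now g. At g = 1.0 and ICC 0.04 the formula gives Φ(−0.32) + Φ(3.09) − 1 = 37%; simulating cluster means gives 38%. Simulated chance of meeting the rule with no effect:

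| Assumed untreated gap | ICC 0.04 | ICC 0.08 |
|---|---|---|
| 0 | 83% | 67% |
| 0.5 | 69% | 55% |
| 1.0 | 38% | 30% |
| 1.5 | 13% | 11% |
| 2.0 | 2.5% | 2.5% |
| 3.0 | about 0% | about 0% |

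At ICC 0.04 the CI half-width is 2.024 × 0.587 = 1.19, so an observed difference within about 2 − 1.19 = 0.81 points passes.

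**Step 4: add the primary contrast.** Now also require depressed-intervention versus depressed-control to favour the intervention (lower TD) at the two-sided 5% level. With no effect, that condition alone holds 2.5% of the time, so the joint rule cannot exceed 2.5%. Simulation with control-cluster effects shared by the two control groups gives 1.2%, 2.1% and 2.3% at gaps of 0, 0.5 and 1.0 (ICC 0.04), and lower values at larger gaps.

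**Step 5: power of the joint rule when the gap is fully closed.**

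| Gap, fully closed | ICC 0.04 | ICC 0.08 |
|---|---|---|
| 3.0 | 83% | 67% |
| 1.7 | 69% | 51% |
| 1.5 | 60% | 42% |
| 1.0 | 31% | 19% |

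These figures move by about a point with the treatment of the standard error. They are for a direct comparison of the named groups, not for the planned three-group model.

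**The case against.** The case for leaving the plan alone has four parts.

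- **The rule concludes equivalence, not convergence.** This is correct: as a statement that two means lie within 2 points, it is sound. A reader might infer that the equivalence test is invalid or that its 83% power is wrong; the documents support neither. But if equivalence is not convergence, the SAP has no criterion for the convergence part of its second objective.
- **The information needed will be reported anyway.** Largely true. The primary contrast is planned, and the model's non-depressed versus depressed-control term comes close to the untreated gap. A careful reader could put them together. What is missing is a prespecified statement of how they combine.
- **The gap is probably not small.** The protocol's premise is that maternal depression impairs child development, and if the planned 3-point effect is to end in equivalence, a gap near 3 is implied. At that size the rule is essentially never met without an effect. This limits the concern but does not remove it, because the 3 points are a detectable treatment difference and no document estimates the untreated gap.
- **A joint rule costs power.** It does when the gap is small, as Step 5 shows. That is the price of a causal claim; the equivalence result itself loses nothing.

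**Conclusion.** The concern holds as a limit on interpretation. The ±2 rule can be met with no intervention effect, and how often depends on an untreated gap that the documents do not give: material below about 1.5 points, negligible at 2 or more. The calculation rests on the SAP's SD, ICC and group size, 11 children per cluster, and the assumed gaps.

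Two stronger readings are not supported. One is that the trial has an 83% chance of a false convergence claim: that figure requires maternal depression to make no difference at all to SDQ-TD, contrary to the trial's premise. The other is that closeness with a non-significant primary contrast proves the intervention did nothing. If a true 1-point gap were fully closed, the primary test would still be non-significant about 62% of the time at ICC 0.04 (simulated power about 38%). The primary analysis is unaffected.

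**What to change.** Keep the equivalence analysis and its margin. Add to SAP 2.4 and 3.1:

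1. Convergence due to the intervention will be concluded only if (a) the 95% CI for depressed-intervention versus non-depressed-control on SDQ-TD lies within ±2, and (b) depressed-intervention versus depressed-control on SDQ-TD favours the intervention at the two-sided 5% level.
2. If only (a) holds, the report will say: *difference within 2 points; not shown to be attributable to the intervention*.
3. The depressed-control versus non-depressed-control difference and its CI will always be reported alongside.
4. These contrasts will come from a model that separates non-depressed women by arm. The three-group model in 3.1.1 pools them, although the rule names the control arm only. SAP section 3 already plans the split as a supplemental analysis.

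No new data are needed. The cost is SAP wording, a four-group version of the model, and lower power to claim convergence when the gap is small. At ICC 0.04 nothing is lost for a fully closed 3-point gap; at ICC 0.08 power there is 67%, already the equivalence rule's own power at that ICC.

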2.5 Intervention

The intervention for moderate-severe perinatal depression being assessed in these trials was the Thinking Healthy Program Peer-Delivered (THPP). THPP is the adapted version (peer-delivered) of the Thinking Healthy Program (THP) originally developed and evaluated (based on delivery by government-

employed LHWs) in Pakistan.⁹ THP has recently been adopted by the World Health Organization (WHO) for global implementation (http://www.who.int/mental_health/maternal-child/thinking_healthy/en/).

THPP comprises up to 14 sessions. The core strategies used by the peers are: active listening, collaboration with the family, guided discovery, homework, and behavioral (patient) activation (identifying and replacing unhealthy behaviors with healthy ones and practicing them).

The intervention begins in the third trimester of pregnancy, and includes ten home-based individual face-to-face sessions and four group-based sessions (given in the LHW women's group meetings) until the sixth month postnatally. Part of the task sharing by peers is to assist LHWs in organizing and conducting these mandatory routine women's groups and to encourage trial participants to attend these sessions. The following description comes from Atif et al. (2019).¹⁰

The extended intervention began after the child was 6 months old and consisted of 18 group 'booster' sessions which were delivered monthly for 6 months, and subsequently every 2 months, until the child was 3 years old. These group sessions provided a safe environment to women to voice their problems, share experiences of childcare, and provide mutual support. The peer volunteers were trained to use culturally-grounded vignettes that served as tools to deliver health and well-being messages. Derived from our qualitative studies, these vignettes depicted a variety of real-life challenges and situations faced by rural women with young children. They aimed to help participants reflect and gain better insight about their own problems and allowed them to share personal experiences of overcoming similar problems. In addition to the narratives, card games containing pictorial illustrations of personal well-being messages were developed. These aimed to challenge unhelpful thinking patterns and behaviour and to replace them with alternative thoughts and behaviour in a fun and interesting way. The sessions aimed to enhance not just maternal well-being but also child-care and development by encouraging mother-infant interaction and play. The intervention provided examples of age-appropriate activities, derived from the WHO's Care for Development Package and encouraged demonstration of these activities during the sessions. While the 'booster' group sessions did not focus on specific strategies to address depression, the peer could still draw on her knowledge and skills of specific psychotherapeutic elements such as behavioural activation when required. A reference manual of the extended THP-P is available at <http://hdrfoundation.org/publications> (under "Training Materials").

2.6 Enhanced Usual Care (Control condition)

In Pakistan, there is non-existent usual care for perinatal depression. The majority of cases of maternal depression either remain unidentified or are classified as 'pregnancy blues'. In part, this is because gynecologists receive no mental health training and are overburdened, resulting in low detection and treatment rates. Therefore, usual care was enhanced in the following ways, for participants in both the intervention and control arms:

- Screening and informing participants about their screening results.

- Informing depressed participants about ways to seek appropriate health care
- Providing the primary health-care centers and gynecologists with the adapted WHO mhGAP treatment guidelines for maternal depression.
- Providing an ‘information about health and stress during pregnancy’ sheet to all pregnant women about how and where to seek health care from, including local Lady Health Workers (LHWs), primary health facilities and tertiary care facilities, both during pregnancy and beyond.

2.7 Time of outcome assessment and visit windows

For all analyses, time will be measured from the date of delivery. Outcome data (depending on the outcome) are collected at 3, 6, 12, 24, and 36 months postnatal. The protocol defined the visit window to be from four weeks (28 days) before to four weeks (28 days) after the scheduled visit date for all mother outcomes. No in-window vs. out-of-window adjustments will be taken into account.

2.8 Data management

Baseline and follow-up outcome data is captured electronically using tablet computers. In addition, process data from peers is also collected. Baseline and outcome data is remotely uploaded as a CSV (comma-separated values) file to the main data server, which run on the software program ODK. Both files are compliant with good clinical practices (including a date and time stamp of original data entry and with an audit trail to document any subsequent changes). Process data is to be collected in paper form, and this is to be manually entered and stored as CSV files using the same data collection platform. THPP quality-related data is also be collected in paper form.

All data, range and consistency checks are performed at weekly intervals separately for each data source. Any queries identified are resolved promptly by the data management team, and the database is updated, maintaining the audit trail. Consistency checks are performed using PostgreSQL, pgAdminIII (ie SQL based queries run on the server). This includes Trial I.D duplication/mismatch, merging two tables in case any changes are made in the questionnaire.

Additional data quality checks are performed by a biostatistician at Duke University.

3 Data Analysis Plan

The main trial paper for both moms and children will focus on the 36-month outcomes solely. Statistical analysis will be conducted according to the CONSORT guidelines.^{11,12} A flow chart will show participation of both perinatally depressed (by intervention arm) and perinatally non-depressed

mothers and their children from recruitment in the third trimester through to 36 months postnatally (Figure 2 is an example, but in practice it will be more detailed). Withdrawals and loss to follow-up will be shown at 36-month post-intervention. All analyses will focus on comparison of three groups: perinataly depressed intervention, perinataly depressed control, and perinataly non-depressed, although we will test for a differential effect by non-depressed in intervention vs. control as a supplemental analysis.

Baseline characteristics of recruited mothers will be reported by study arm for perinataly depressed women, and overall for perinataly non-depressed women. Continuous variables will be summarized by means and standard deviation (SD), or medians and the 25th and 75th percentile, if needed. Categorical variables will be summarized by counts and percentages. Distributions of outcomes will also be explored using graphical techniques such as box plots and histograms.

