The sampling unit within each cluster is the mother-child dyad. Women in the last trimester of pregnancy residing in one of the 40 study clusters will be identified through community surveillance normally conducted by community health workers (CHW). CHWs are utilized in most lower/middle income countries to deliver basic maternal and child health services. In Pakistan, each CHW covers 100 households and is informed of every pregnancy. Our research team has a long-standing relationship with the CHWs in the study areas. The CHWs will liaise with the research field staff which will seek informed consent from the pregnant woman and screen her for depression using the PHQ-9. We will offer enrollment to each woman who screens positive for depression and the first woman who subsequently screens negative. As a result, every cluster in the intervention and control arms will include women who score above and below the depression screening cutoff. Due to the community nature of the intervention, we anticipate that non-depressed women in the intervention clusters will benefit from the trial. Women who are suicidal, psychotic or already under depression treatment will be referred to mental health specialist care and excluded from the study. If the infant is born with congenital abnormalities or with other significant health problems, the mother-child dyad will be excluded.

Our data collection protocols that begin prenatally through 6 months postpartum will be synchronized with the main SHARE study (see Figure 1). After 6 months, SHARE ends and we continue the SHARE CHILD data collection. Interviews will be scheduled at 3, 6, 12, 24 and 36 postpartum month milestones for each mother-child dyad (see Table 1).

Table 1: Timeline of SHARE CHILD assessments

Breastfeeding		✓	✓	✓		
MSPSS	✓	✓	✓	✓	✓	✓
PHQ-9	✓	✓	✓			
WHO-DAS	✓	✓	✓			
Sociodemographic questions	✓			✓	✓	✓
BAYLEY				✓	✓	✓
HOME		✓	✓	✓	✓	✓
ASQ SE			✓	✓	✓	✓
Vineland			✓	✓	✓	✓
Height/Weight		✓	✓	✓	✓	✓
Maternal postnatal attachment		✓	✓			
Maternal efficacy		✓	✓			
Cohen PSS		✓	✓	✓	✓	✓
IPV	✓	✓		✓	✓	✓
CISR		✓	✓			✓
SDQ						✓
Risk game	✓			✓		
Stroop test	✓			✓		
Autonomy questions	✓			✓	✓	✓
A day in life		✓	✓			
Father involvement in child care	✓	✓	✓	✓	✓	✓

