3.1 Analysis of primary and secondary outcomes

The primary analyses are designed as intention-to-treat and will be conducted using Stata version 16. Maternal and child outcomes are listed in Table 1. ***For all outcomes, the 36-month time point is considered primary.*** The primary child outcome is the Total Difficulties score from the Strengths and Difficulties Questionnaire (SDQ-TD). The primary maternal outcome is the Patient Health Questionnaire (PHQ-9). The secondary outcomes are detailed in Table 1. Of note, the Bayley scores (secondary outcome) will be scaled using the provided U.S. normed scales.

Separate outcome analysis will be conducted for mothers and for children. In both cases, data from perinataly depressed (by intervention arm) and perinataly non-depressed participants will be analysed jointly using linear mixed effects models so that all comparisons of interest can be estimated from the same model. The **identity link** will be used for **continuous outcomes** in order to estimate differences in mean outcomes.

Since our main predictor of interest is the treatment arm indicator (with non-depressed as a separate “arm”), which is related to the sampling variable, the primary analyses will be unweighted, and we will use restricted maximum likelihood (REML). If the model fails to converge after 50 iterations, then we use maximum likelihood. In addition, the between-within method will be used to apply small-sample corrections in the mixed effects framework.¹³ The reason for not using the sampling weights is that the sampling scheme is related to the main predictor of interest, so weighting should lead to minimal, if any, changes in the main results of interest. In addition, not using the sampling weights simplifies the modeling process and allows us to use estimation procedures (REML) shown to reduce bias, in addition to allowing us to use small-sample corrections on the models.

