GEE analyses with a **log-link** and **Poisson distribution** will be used for **binary outcomes** in order to estimate prevalence ratios. The GEE analyses will apply the Kauermann-Carroll small-sample corrections with a t-test for inference.^{14,15} The GEE analyses will take into account clustering using an exchangeable working correlation matrix, and robust standard errors to account for potential model misspecification. All mixed models will include village cluster as a random intercept to account for the clustered study design. (Note that a separate random intercept for each group [intervention, control, non-depressed] was considered and formulated in section 3.1.1.1, but model convergence issues led us to revert to a single random intercept for cluster.) Additionally, clustering by peer group within the intervention arm will be potentially taken into account by adding an additional random intercept for each peer group.

Primary analyses of outcomes measured at a single follow-up time point are designed to include the following fixed factor variables: group (non-depressed, depressed intervention, depressed control), strata (11 Union councils), and any variables found to be imbalanced by loss to follow-up or at baseline (determined using $p < 0.10$). Under the assumption that those covariates explain the missing data mechanism, we will obtain valid estimates of the intervention effects using the complete case data (i.e. without the need for imputation or an alternative method).¹⁶ If there are concerns or evidence that covariates cannot explain the nature of the missingness (i.e. if the data are missing not at random), we will perform a series of sensitivity analyses based on the pattern mixture approach.¹⁷

Model assumptions will be assessed using examination of the residuals from the model and tests for linearity. In the presence of a ceiling or floor effect, we will also model the outcome using mixed effects tobit regression, which may allow us to more appropriately model the mean in such a situation.

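### The three-group primary model assumes no carryover to non-depressed women, removes part of any carryover from the primary effect, and cannot estimate the equivalence contrast defined in SAP 2.4

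*SAP*

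**What the plan says.** SAP section 3 sets the frame: "All analyses will focus on comparison of three groups: perinataly depressed intervention, perinataly depressed control, and perinataly non-depressed". The same sentence adds a supplemental test of non-depressed women in intervention against control clusters. Section 3.1 analyses all participants jointly "so that all comparisons of interest can be estimated from the same model". On the random part it reports that "model convergence issues led us to revert to a single random intercept for cluster". Section 3.1.1 gives one dummy variable for non-depressed women, not split by arm, and the Stata code uses a three-level arm factor, union council and one random intercept per village cluster.

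Other passages treat the non-depressed women of the two arms as different groups:

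- Protocol section 2 enrols non-depressed women partly to "identify potential positive externalities to non-depressed women in the intervention arm".
- Protocol 3.1 states that "we anticipate that non-depressed women in the intervention clusters will benefit from the trial".
- SAP 2.1 refers to the "reference group of perinatally non-depressed mothers and children as well as, secondarily, to determine whether there are any carryover effects", with no arm limit on that reference.
- SAP 2.4 defines the secondary hypothesis as "equivalence between children of perinatally depressed mothers in the intervention arm and perinatally non-depressed mothers in the control arm". It also gives 80% power for a 1.7-point carryover effect between the two non-depressed groups.

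Baseline data in section 3 are to be shown by arm for depressed women "and overall for perinataly non-depressed women".

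**The concern.** Depressed and non-depressed women in a village share the random intercept, so the model uses the non-depressed women as a within-village reference. It also holds their mean equal across arms. If the intervention helps non-depressed women, their better scores in intervention villages are taken as a sign that those villages were better anyway. Part of that difference is then subtracted from the primary effect. In effect, the analysis adjusts for a cluster-level covariate that the treatment may have changed.

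Two things are at stake. The primary estimate would be biased, with an interval that is too confident, in the situation the protocol anticipates. And whatever the size of carryover, a three-level factor has no non-depressed-control mean, so neither the equivalence contrast nor the carryover contrast of section 2.4 can be taken from the model that is meant to supply every comparison.

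**Working it through.** **Inputs.** From SAP 2.4: 40 clusters, 20 per arm, 11 strata; SD 5.2; ICC 0.04 to 0.08; two-sided 5%; primary effect 3 points; equivalence margin ±2; detectable carryover 1.7. Women per group per cluster, m: 220/20 = 11 (equivalence calculation) and 480/40 = 12 (primary calculation). The stated 20% loss gives 560 × 0.8 = 448, or 11.2 per cluster, which lies in the same range. Assumed: nine strata of 4 clusters and two of 2, equal m in every cluster, and 28 degrees of freedom (40 − 11 − 1; critical value 2.048).

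**The SAP's own powers.** For an unpooled two-group comparison, SE = SD·√{2[1+(m−1)ICC]/(20m)}. At m = 11 and ICC 0.04, SE = 5.2·√(2.8/220) = 0.587.

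- Equivalence: 2Φ(2/0.587 − c) − 1 = 85% with c = 1.96 and 83% with c = 2.048. SAP: 83%.
- Carryover 1.7: Φ(1.7/0.587 − c) = 83% and 80%. SAP: 80%.

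Section 2.4 was therefore computed for four arm-specific groups, not for the pooled model.

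**Bias in the primary contrast.** With balanced clusters, the generalised least squares (GLS) estimate from the three-group model equals the depressed contrast minus w times the non-depressed contrast, where w = ICC/[ICC + (1−ICC)/m]. Its expectation is the true effect − w × carryover. An exact GLS calculation with strata gives the same result; the four-group model has zero bias.

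| ICC | w (m = 11) | w (m = 12) |
|---|---|---|
| 0.01 | 0.10 | 0.11 |
| 0.02 | 0.18 | 0.20 |
| 0.04 | 0.31 | 0.33 |
| 0.08 | 0.49 | 0.51 |

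A true 3.0 with carryover 1.0 reads 3 − 0.31 = 2.69 (ICC 0.04, m = 11) to 3 − 0.51 = 2.49 (ICC 0.08, m = 12). With carryover 1.7 it reads 2.47 to 2.13.

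**Coverage and power** (REML simulation, 1000 runs per cell, m = 11):

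| Carryover | ICC 0.04 | ICC 0.08 | ICC 0.01–0.02 |
|---|---|---|---|
| 0 | about 96% | about 96% | – |
| 1.0 | 92% | 87% | 94–95% |
| 1.7 | 80% | 68% | 86–91% |

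The four-group model gave 94–98% throughout. GLS with known variances gives 93%/88% at carryover 1.0 and 86%/73% at 1.7. REML is worse because unmodelled carryover inflates the fitted ICC (0.04 reads 0.046–0.057), which raises the mean share removed to about 34–39% at ICC 0.04 and 52–56% at 0.08.

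Power for 3 points at carryover 1.7 is 95–99% by GLS and 91–97% by REML. For a true effect of 1.7 with carryover 1.0, power falls from 80% (four-group) to 67% (three-group) at ICC 0.04, and from 69% to 52% at 0.08.

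If the cluster effects of the two groups correlate only 0.5, about 28–34% (ICC 0.04) or 45–48% (ICC 0.08) of carryover is still removed.

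**Equivalence.** The pooled contrast differs from the one defined in 2.4 by carryover × (1 + w)/2, which is 66–76% of carryover. At 1.7 that is 1.1 to 1.3 points of a ±2 margin. With depressed-intervention truly equal to non-depressed-control (m = 11, 28 df), the chance of concluding equivalence is:

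| | ICC 0.04 | ICC 0.08 |
|---|---|---|
| Four-group, any carryover | 83% | 66% |
| Pooled, carryover 0 | 99% | 99% |
| Pooled, carryover 1.0 | 84% | 78% |
| Pooled, carryover 1.7 | 48% | 35% |

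**Binary PHQ-9.** The remission rates in 2.4 imply prevalence 35% against 55%, a ratio of 0.636. Solving the expected estimating equations of the planned GEE, with an assumed non-depressed prevalence of 15–25% and an assumed carryover ratio of 0.8 (neither is in the documents), gives 0.67–0.69 at working correlation 0.05–0.07 and 0.65–0.66 at 0.02. The four-group model returns 0.636.

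**The case against.** No passage states an expected size of carryover: 1.7 is a detectable difference, and SAP 2.1 asks only whether there is any. For small carryover the SAP's model is the better estimator. Since SE₃² = SE₄²(1 − w²), its mean squared error is lower until carryover reaches SE₄, about 0.59 points at ICC 0.04 and 0.67 at ICC 0.08 (m = 11). At carryover 0.5, GLS coverage is still 94–95%. This stands, and it is why every bias figure here is conditional on carryover.

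The ICC left after adjusting for union council may be below 0.04–0.08. This also stands; at 0.01–0.02 the share removed is only 10–20%.

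The SAP's between-within method may give far more than 28 degrees of freedom. That would lift the four-group powers slightly (85% and 83% above), but it would lower, not raise, the three-group coverage under carryover.

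The bias runs against the intervention when carryover is beneficial, so it does not create a false claim of benefit. That is true, but harmful carryover would inflate the effect.

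The supplemental carryover test is a real safeguard only in part. It has no stated model, leaves the primary estimate unchanged, and comes with no rule for acting on it. Its power at carryover 1.0 is 37% (ICC 0.04) or 29% (ICC 0.08), so a non-significant result would not justify pooling.

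None of these points touches the conflict over the reference group.

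**Conclusion.** The concern holds and should be fixed. The mismatch between section 2.4 (non-depressed control), section 2.1 (no arm limit) and sections 3 and 3.1.1 (both arms pooled) is unconditional: the specified model cannot produce the stated equivalence contrast. The bias in the primary effect is conditional on carryover. It is 31–51% of whatever carryover occurs at the SAP's ICCs, less at lower ICC, and nil if carryover is zero. The harm is an attenuated estimate with undercoverage, and lost power at effects smaller than planned; the power claim for 3 points survives. The algebra is secure, but the practical size rests on a carryover effect that the documents anticipate without quantifying.

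**What to change.** - Use a four-level group factor (depressed or non-depressed, by intervention or control) in the primary mixed and GEE models.
- Name three contrasts: depressed-intervention versus depressed-control (primary); depressed-intervention versus non-depressed-control (equivalence, as in 2.4); non-depressed-intervention versus non-depressed-control (carryover).
- Make SAP 2.1, 2.4 and 3 agree on the equivalence reference.
- Report non-depressed baseline data by arm.
- Keep the pooled three-group model as supplementary.

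The cost is SAP wording and one more factor level; no new data are needed. At m = 11 the primary standard error rises from 0.557 to 0.587 (ICC 0.04) or from 0.580 to 0.665 (ICC 0.08). The equivalence standard error rises more, from 0.442 to 0.587 or from 0.444 to 0.665, because the gain from pooling is given up. At the SAP's own ICC of 0.04 the stated 83% and 80% powers are kept, and power for 3 points stays above 99%. At ICC 0.08 equivalence power is 66%, a limit that the SAP should state.
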